#### **8.4. Medical History**

Medical history will be coded using the MedDRA 22.1 and listed by dose level of RC-P, route of administration (IM or IV), system organ class (SOC), and preferred term (PT) for Safety Analysis Set. For data presentation, SOC will be ordered alphabetically, with PT sorted by decreasing frequency in the final dose of IM.

#### **8.5. Prior and Concomitant Medications**

Prior and concomitant medications will be coded using the World Health Organization (WHO) Drug Dictionary and will be summarized separately by dose level of RC-P and route of administration (IM or IV) for the Safety Analysis Set.

Prior medications are defined as those medications taken prior to Study Day 1. Concomitant medications are defined as medications taken at any time on or after Study Day 1. If any medications were taken prior to Study Day 1 and continued to or after Study Day 1, it will be counted as both prior and concomitant medications. Like AEs, prior and concomitant definitions for medications will be derived after taking into consideration any partial or completely missing start and end dates (See [Appendix I](#)).

Listings of prior medications and concomitant medications will be provided separately.

#### **8.6. Protocol Deviations**

Major protocol deviations will be summarized by dose level of RC-P and route of administration (IM or IV) using the Safety Analysis Set. All protocol deviations will be listed.

Jazz Pharmaceuticals Ireland Limited  
Statistical Analysis Plan – Protocol JZP458-201

## **9. EFFICACY**

### **9.1. Primary Efficacy Endpoint and Analysis**

#### **9.1.1. Primary Efficacy Endpoint**

The primary efficacy endpoint of the study is the response rate, defined as the proportion of patients with the last 72-hour NSAA level  $\geq 0.1$  IU/mL during the first course of IM administration of RC-P. Patients in both Part A Cohort 1 and Cohort 2 at the final IM RC-P dose level will be included. Depending on the RC-P start day for a patient, this could be predose 4 if the first course of RC-P started on a Monday; predose 6 if the first course of RC-P started on a Wednesday; or predose 5 if the first course of RC-P started on a Friday.

#### **9.1.2. Analysis of the Primary Efficacy Endpoint**

The primary efficacy endpoint will be estimated using the Efficacy Analysis Set for patients administered the final IM RC-P dose level with at least one 72-hour NSAA assessment collected within the protocol defined sample collection window ( $\pm 2$  hours) in Course 1 of Part A. The last observed 72-hour NSAA assessment collected within the protocol defined sample collection window ( $\pm 2$  hours) in Course 1 will be used in the calculation of the primary efficacy endpoint. Missing data will not be imputed. The response rate, along with the 95% Wald CI will be provided. The primary efficacy endpoint will be met if the lower bound of the 95% CI of the response rate exceeds 90%.

#### **9.1.3. Sensitivity Analyses**

A sensitivity analysis will be performed to assess COVID-19 impact on the primary efficacy endpoint. Patients in the Efficacy Analysis Set who missed any PK sample collections in Course 1 due to COVID-19 will be excluded from the analysis. The response rate for this subset along with the 95% Wald CI will be provided.

#### **9.1.4. Subgroup Analyses**

The primary efficacy endpoint will be analyzed for the patient subgroups specified in [Section 7.4](#).

### **9.2. Secondary Efficacy Endpoints and Analyses**

#### **9.2.1. Key Secondary Efficacy Endpoint**

The key secondary efficacy endpoint of the study is the response rate, defined as the proportion of patients with the last 48-hour NSAA level  $\geq 0.1$  IU/mL during the first course of IM administration of RC-P.

The key secondary efficacy endpoint will be analyzed using the Efficacy Analysis Set for patients administered the final IM RC-P dose level with at least one 48-hour NSAA assessment collected within the protocol defined sample collection window ( $\pm 2$  hours) in Course 1 of Part A. The last observed 48-hour NSAA assessment collected within the protocol defined sample collection window ( $\pm 2$  hours) in Course 1 will be used in the calculation of the key secondary efficacy endpoint. Missing data will not be imputed. The response rate, along with the 95% Wald CI will

Jazz Pharmaceuticals Ireland Limited  
Statistical Analysis Plan – Protocol JZP458-201

be provided. The key secondary efficacy endpoint will be met if the lower bound of the 95% CI of the response rate exceeds 90%.

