8.7.2. Secondary Efficacy Endpoints and Analyses

Secondary efficacy endpoints include the following from Part A of the study:

- Key secondary efficacy endpoint: Proportion of patients with the last 48-hour NSAA level ≥ 0.1 IU/mL during the first course of IM administration of RC-P
- Proportion of patients with the last 48-hour level ≥ 0.4 IU/mL during the first course of IM administration of RC-P
- Proportion of patients with the last 72-hour NSAA level ≥ 0.4 IU/mL during the first course of IM administration of RC-P

8.7.2.1. Key Secondary Efficacy Endpoint: Proportion of Patients with the Last 48-hour NSAA Level ≥ 0.1 IU/mL during the First Course of IM Administration of RC-P

The proportion of patients with the last 48-hour NSAA level ≥ 0.1 IU/mL during the first course of IM administration of RC-P will be analyzed using the same methodology as the primary efficacy endpoint using the Efficacy Analysis Set for patients administered the final IM RC-P dose level with at least one 48-hour NSAA assessment collected within the protocol-defined sample collection window (± 2 hours) in Course 1 of Part A. The response rate, along with the 95% Wald CI will be provided.

8.7.2.2. Proportion of Patients with the Last 48-hour NSAA Level ≥ 0.4 IU/mL during the First Course of IM Administration of RC-P

The proportion of patients with the last 48-hour NSAA level ≥ 0.4 IU/mL during the first course of IM administration of RC-P will be analyzed. This analysis will use the same methodology as the primary efficacy endpoint using the Efficacy Analysis Set for patients administered the final IM RC-P dose level with at least one 48-hour NSAA assessment collected within the protocol-defined sample collection window (± 2 hours) in Course 1 of Part A. The response rate, along with the 95% Wald CI will be provided.

8.7.2.3. Proportion of Patients with the Last 72-hour NSAA Level ≥ 0.4 IU/mL during the First Course of IM Administration of RC-P

The proportion of patients with the last 72-hour NSAA level ≥ 0.4 IU/mL during the first course of IM administration of RC-P will be analyzed. This analysis will use the same methodology as the primary efficacy endpoint using the Efficacy Analysis Set for patients administered the final

IM RC-P dose level with at least one 72-hour NSAA assessment collected within the protocol-defined sample collection window (± 2 hours) in Course 1 of Part A. The response rate, along with the 95% Wald CI will be provided.

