## 5.3. Power and Sample Size Considerations

For Part A of the study, 98 patients administered the final IM dose level are planned.

For the final IM RC-P dose level, 13 evaluable patients are planned in Part A Cohort 1 (IM RC-P Dose Confirmation), and approximately 85 patients are planned in Cohort 2 (IM Expansion) to obtain 98 patients in total at the final dose in Part A for the primary efficacy analysis of the IM administration route.

The sample size of 13 evaluable patients in Part A Cohort 1 provides at least 80% posterior probability of the true response rate  $\geq 96\%$  given 100% response rate in Cohort 1 and non-informative neutral beta prior with  $\alpha = \beta = 1/3$ .

Since the primary efficacy endpoint is considered to be met if the lower bound of the 95% Wald confidence interval (CI) of the response rate exceeds 90%, the final sample size is planned as 98 patients which provides 83% probability that the lower bound of the 95% Wald CI exceeds 90%, assuming a true response rate of 96% for the primary efficacy endpoint and a 5% drop out rate. Furthermore, with a sample size of 98 patients, the probability of observing at least one adverse events (AE) related to asparaginase with an incidence as low as 3% is 95%.

For the primary efficacy assessment at the primary analysis, a minimum of 93 patients in the Efficacy Analysis Set are required. This means at least 93 patients received at least one dose of the final IM RC-P dose level, and had at least one 72-hour NSAA assessment collected within the protocol-defined sample collection window ( $\pm 2$  hours) in Course 1. If fewer than 93 out of 98 patients have the necessary data, additional patients will be enrolled to ensure 93 patients for analysis.

One interim analysis with 51 patients is planned. At the interim analysis, a sample size of 51 patients provides 70% probability that the lower bound of the 95% CI exceeds 90% under the assumption of a 96% true response rate and a 5% drop out rate. The probability of observing at least one AE related to asparaginase with an incidence as low as 3% is 79% with 51 patients.

Similar to the primary analysis, a minimum of 48 patients in the Efficacy Analysis Set for the primary efficacy assessment are necessary for the interim analysis. If fewer than 48 out of 51 patients have the necessary data, additional patients will be enrolled to ensure 48 patients for analysis.

Jazz Pharmaceuticals Ireland Limited  

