### **7.3. Hypotheses Testing, Level of Significance and Multiplicity Adjustment**

No formal statistical testing is planned for this study and thus no multiplicity adjustment is applicable.

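### The 48-hour key secondary endpoint has its own 90% pass rule with no stated order after the 72-hour primary (minor)

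*SAP*

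**What the plan says.** SAP 9.1.2 sets the primary criterion for the 72-hour rate: "The primary efficacy endpoint will be met if the lower bound of the 95% CI of the response rate exceeds 90"%. SAP 9.2.1 repeats it for the 48-hour rate: "The key secondary efficacy endpoint will be met if the lower bound of the 95% CI of the response rate exceeds 90"%. Neither section refers to the other. The remaining secondary endpoints (SAP 9.2.2, the 0.4 IU/mL thresholds) get an estimate and interval only.

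SAP 7.3 reads: "No formal statistical testing is planned for this study and thus no multiplicity adjustment is applicable". It sets no order of endpoints.

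Protocol 8.7.2.1 has the key secondary analysed by the primary's method and then says "The response rate, along with the 95% Wald CI will be provided". It spells out no separate criterion and no order. SAP 5.5 ties early stopping for efficacy to the primary alone and does not mention the key secondary.

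SAP 5.3 sizes the trial on the primary's rule. It describes the planned total of 98 as a number "which provides 83% probability that the lower bound of the 95% Wald CI exceeds 90"%. Behind that figure stand a 96% true 72-hour rate and 5% dropout.

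**The concern.** A sentence that says an endpoint will be met if an interval bound clears a threshold is a decision rule. It has a false-pass probability whether or not it is called a test. The plan has two such rules, one labelled primary and one key secondary, and says nothing about what the second may claim if the first fails. A trial that misses its 72-hour primary could still report its key secondary as met against the same 90% bar. SAP 7.3 does not settle this, because it disclaims testing while 9.1.2 and 9.2.1 keep their pass rules. What is at stake is how a 'met' statement on the key secondary may be read in a study that Protocol 3.2 calls pivotal. The primary's own criterion is not affected.

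**Working it through.** **Inputs from the documents.** Both rules need the lower bound of a two-sided 95% Wald interval to exceed 90%. At the primary analysis "a minimum of 93 patients in the Efficacy Analysis Set are required"; at the interim, "a minimum of 48 patients in the Efficacy Analysis Set for the primary efficacy assessment are necessary for the interim analysis". The planning rate is 96%.

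**Assumptions (not in the documents).** The 48-hour analysed number is also 93. The true 48-hour rate and the dependence between the two responses are varied below.

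**1. Pass counts.** Find the smallest r with r/n − 1.96·√[(r/n)(1 − r/n)/n] > 0.90.
- n = 93: 88/93 gives 0.9004 (pass); 87/93 gives 0.8856 (fail). Need at least 88.
- n = 48: 46/48 gives 0.9018 (pass); 45/48 gives 0.8690 (fail). Need at least 46.

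**2. Reproduce the plan's figures** with the exact binomial tail P(X ≥ r).
- n = 93, rate 96%: 0.831 (stated 83%).
- n = 93, rate 94%: 0.512 (stated 51%, Protocol 8.3).
- n = 48, rate 96%: 0.699 (stated 70%).

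All three agree.

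**3. False-pass probability of one rule.** At a true rate of 90% and n = 93, P(X ≥ 88) = 0.0870.

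**4. At least one false 'met' when both true rates are 90%, n = 93.** This is 2 × 0.0870 − P(both pass). The dependence is modelled as a latent normal correlation between a patient's 72-hour and 48-hour values.

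| Dependence | P(both pass) | At least one false 'met', no order | With fixed order |
|---|---|---|---|
| Correlation 0 | 0.0076 | 0.167 | 0.087 |
| Correlation 0.5 | 0.0147 | 0.159 | 0.087 |
| Correlation 0.9 | 0.0354 | 0.139 | 0.087 |
| Strictly nested (same patients respond) | 0.0870 | 0.087 | 0.087 |

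If 0.9 is instead taken as the correlation between the two pass statistics, the figure is 0.115.

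**5. False 48-hour claim under strict nesting, true 48-hour rate 90%, n = 93.** With no order it is 0.087 whatever the 72-hour rate. With a fixed order, nesting means that both rules pass exactly when the 72-hour rule passes, so the probability is the 72-hour tail:
- 72-hour rate 90%: 0.087 (no change).
- 72-hour rate 88%: 0.027.
- 72-hour rate 85%: 0.003.

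**6. What the order withholds.** With assumed true rates of 96% (72-hour) and 99% (48-hour), nested, P(48-hour met, 72-hour not met) is 0.169 at n = 93. By simulation over both looks it is 0.129. Both true rates exceed 90%, so these are correct 48-hour claims.

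**The case against.** The strongest case against is that this is a single-arm study whose SAP disclaims multiplicity control, and the key secondary triggers no stated decision. A failed primary would be reported beside it. That stands, and it is why the point is minor.

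Four stronger readings are tempting, and the documents do not support them.

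- *That the SAP invented a criterion the protocol lacks.* Protocol 8.7.2.1 adopts the primary's method, and the primary's method in Protocol 8.7.1 includes the 90% rule. The SAP can fairly be read as spelling out what the protocol carries over. What is missing from both is the order.
- *That a 'met' 48-hour result after a failed primary is a false claim about 17% of the time.* That figure assumes true rates of 96% and 99%. The 48-hour claim is then true, so 17% is the cost of a fixed order and not a harm of its absence.
- *That the missing order drives the false-claim rate to 16.4% over the two looks.* That rise comes from the repeated look, and it lets an interim key-secondary pass stand while the trial continues. SAP 5.5 gives the key secondary no interim role. If it is judged once, where the trial stops, the nested figures are 12.1% (72-hour rate 88%) and 9.6% (85%).
- *That the 72-hour rate must be the lower one.* Every 72-hour trough in Protocol Appendix 2 follows a Friday dose, and Protocol 3.1.3.1 allows the Friday dose to differ. The ordering of the two rates is plausible but not given.

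Nesting is not assured either. The last 48-hour and last 72-hour samples follow different doses; for a Monday start they are predose 6 and predose 4. This is why the excess in step 4 cannot be ruled out.

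**Conclusion.** The point holds as a minor one. The plan states two pass rules and no order between them, and SAP 7.3 is at odds with both. At n = 93 and true rates of 90%, the chance of at least one false 'met' is about 14% to 17% (assumed patient-level latent correlation 0.9 down to 0), against 8.7% with a fixed order. Under strict nesting there is no excess over 8.7%. A fixed order would still lower the false 48-hour claim rate from 8.7% to about 2.7% or 0.3% if the 72-hour rate is 88% or 85%.

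The 48-hour rate, the 48-hour analysed number and the correlation are assumptions. The 8.7% itself belongs to the Wald rule, and a fixed order corrects neither that nor the repeated look. The plan's 83%, 70% and 51% are right and unaffected.

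**What to change.** In SAP 9.2.1, state that the key secondary is declared met only if the primary is met at the same analysis, and that otherwise its rate and interval are descriptive. In SAP 7.3, replace the statement that no multiplicity adjustment applies with the fixed order: primary first, then key secondary.

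The cost is two sentences, plus the loss of a formal 48-hour claim whenever the primary fails. At the assumed 96% and 99% that is about 17% of trials at n = 93, or 13% over both looks. The 48-hour rate and its interval are still reported.

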### **9.2.2. Other Secondary Efficacy Endpoints**

Other secondary efficacy endpoints in Part A include the following:

- Proportion of patients with the last 48-hour NSAA level  $\geq 0.4$  IU/mL during the first course of IM administration of RC-P
- Proportion of patients with the last 72-hour NSAA level  $\geq 0.4$  IU/mL during the first course of IM administration of RC-P

#### **9.2.2.1. Proportion of Patients with the Last 48-hour NSAA Level $\geq 0.4$ IU/mL during the First Course of IM Administration of RC-P**

The proportion of patients with the last 48-hour NSAA level  $\geq 0.4$  IU/mL during the first course of IM administration of RC-P will be analyzed using the Efficacy Analysis Set for patients administered the final IM RC-P dose level with at least one 48-hour NSAA assessment collected within the protocol defined sample collection window ( $\pm 2$  hours) in Course 1 of Part A. The last observed 48-hour NSAA assessment collected within the protocol defined sample collection window ( $\pm 2$  hours) in Course 1 will be used in the calculation of this endpoint. Missing data will not be imputed. The response rate, along with the 95% Wald CI will be provided.

#### **9.2.2.2. Proportion of Patients with the Last 72-hour NSAA Level $\geq 0.4$ IU/mL during the First Course of IM Administration of RC-P**

The proportion of patients with the last 72-hour NSAA level  $\geq 0.4$  IU/mL during the first course of IM administration of RC-P will be analyzed using the Efficacy Analysis Set for patients administered the final IM RC-P dose level with at least one 72-hour NSAA assessment collected within the protocol defined sample collection window ( $\pm 2$  hours) in Course 1 of Part A. The last observed 72-hour NSAA assessment collected within the protocol defined sample collection window ( $\pm 2$  hours) in Course 1 will be used in the calculation of this endpoint. Missing data will not be imputed. The response rate, along with the 95% Wald CI will be provided.

### **9.2.3. Sensitivity analyses**

A sensitivity analysis will be performed to assess COVID-19 impact on the key secondary efficacy endpoint. Patients in the Efficacy Analysis Set who missed any PK sample collections in Course 1 due to COVID-19 will be excluded from the analysis. The response rate for this subset along with the 95% Wald CI will be provided.

### **9.2.4. Subgroup Analyses**

The key and other secondary efficacy endpoints will be analyzed for the patient subgroups specified in [Section 7.4](#).

## **9.3. Exploratory Efficacy Endpoints and Analyses**

Exploratory efficacy endpoints include the following from Part B of the study:

Jazz Pharmaceuticals Ireland Limited  
Statistical Analysis Plan – Protocol JZP458-201

- Proportion of patients with the last 48-hour NSAA level  $\geq 0.1$  IU/mL during the first course of IV administration of RC-P
- Proportion of patients with the last 72-hour NSAA level  $\geq 0.1$  IU/mL during the first course of IV administration of RC-P
- Proportion of patients with the last 48-hour NSAA levels  $\geq 0.4$  IU/mL during the first course of IV administration of RC-P
- Proportion of patients with the last 72-hour NSAA level  $\geq 0.4$  IU/mL during the first course of IV administration of RC-P

**9.3.1. Proportion of patients with the Last 48-hour NSAA level  $\geq 0.1$  IU/mL during the first course of IV administration of RC-P**

The proportion of patients with the last 48-hour NSAA level  $\geq 0.1$  IU/mL during the first course of IV administration of RC-P will be analyzed using the Efficacy Analysis Set for patients administered the final IV RC-P dose level with at least one 48-hour NSAA assessment collected within the protocol defined sample collection window ( $\pm 2$  hours) in Course 1 of Part B. The last observed 48-hour NSAA assessment collected within the protocol defined sample collection window ( $\pm 2$  hours) in Course 1 will be used in the calculation of this endpoint. Missing data will not be imputed. The response rate, along with the 95% CI will be provided.

**9.3.2. Proportion of patients with the Last 72-hour NSAA level  $\geq 0.1$  IU/mL during the first course of IV administration of RC-P**

The proportion of patients with the last 72-hour NSAA level  $\geq 0.1$  IU/mL during the first course of IV administration of RC-P will be analyzed using the Efficacy Analysis Set for patients administered the final IV RC-P dose level with at least one 72-hour NSAA assessment collected within the protocol defined sample collection window ( $\pm 2$  hours) in Course 1 of Part B. The last observed 72-hour NSAA assessment collected within the protocol defined sample collection window ( $\pm 2$  hours) in Course 1 will be used in the calculation of this endpoint. Missing data will not be imputed. The response rate, along with the 95% CI will be provided.

**9.3.3. Proportion of patients with the Last 48-hour NSAA level  $\geq 0.4$  IU/mL during the first course of IV administration of RC-P**

The proportion of patients with the last 48-hour NSAA level  $\geq 0.4$  IU/mL during the first course of IV administration of RC-P will be analyzed using the Efficacy Analysis Set for patients administered the final IV RC-P dose level with at least one 48-hour NSAA assessment collected within the protocol defined sample collection window ( $\pm 2$  hours) in Course 1 of Part B. The last observed 48-hour NSAA assessment collected within the protocol defined sample collection window ( $\pm 2$  hours) in Course 1 will be used in the calculation of this endpoint. Missing data will not be imputed. The response rate, along with the 95% CI will be provided.

**9.3.4. Proportion of patients with the Last 72-hour NSAA level  $\geq 0.4$  IU/mL during the first course of IV administration of RC-P**

The proportion of patients with the last 72-hour NSAA level  $\geq 0.4$  IU/mL during the first course of IV administration of RC-P will be analyzed using the Efficacy Analysis Set for patients

Jazz Pharmaceuticals Ireland Limited  
Statistical Analysis Plan – Protocol JZP458-201

administered the final IV RC-P dose level with at least one 72-hour NSAA assessment collected within the protocol defined sample collection window ( $\pm 2$  hours) in Course 1 of Part B. The last observed 72-hour NSAA assessment collected within the protocol defined sample collection window ( $\pm 2$  hours) in Course 1 will be used in the calculation of this endpoint. Missing data will not be imputed. The response rate, along with the 95% CI will be provided.

Jazz Pharmaceuticals Ireland Limited  
Statistical Analysis Plan – Protocol JZP458-201

## 10. SAFETY

Safety analyses will be summarized by dose level of RC-P, and route of administration (IM or IV) using the Safety Analysis Set. No formal statistical testing will be performed for the safety analyses.

